8.1 Eligibility criteria

Inclusion criteria:

- Patients with manifest PAD stages II-IV according to Fontaine or healthy volunteers
- Adults (>18 years) who are able to give their consent

Definition of patient group:

- Patients with PAD IIa/IIb/III/IV according to Fontaine who come in for a routine presentation of the vascular surgery consultation hours.

Definition of healthy volunteer group:

- no PAD previously known
- no diabetes mellitus previously known
- no chronic renal insufficiency previously known
- no symptoms in the sense of a Claudicatio intermittens
- ABI with normal value

Exclusion criteria:

- Patients with PAD stage I according to Fontaine
- Healthy volunteers with pre-existing diabetes mellitus, chronic renal failure, or abnormal ABI
- Underage persons
- Missing consent form
- Exclusion due to safety concerns of the study physician (patient with a physical, mental or psychiatric illness which, in the opinion of the study physician, would compromise the safety of the patient or the quality of the data and thus make the patient an unsuitable candidate for the study)

8.2 Number of cases

A valid calculation of the number of cases is not possible because of the novelty of the reconstruction procedure and due to the study design as a pilot study with explorative character. For the exploration of the planned research question, a study collective of 8

study participants is aimed for. Two healthy volunteers, two patients in PAD stage II, two patients in stage III and two patients in stage IV according to Fontaine will be examined. One male and one female will be included per stage to represent both genders.

8.3 Recruitment routes and measures

Patients will be informed of the opportunity to participate in the study during a routine consultation in the vascular surgery department. Healthy volunteers will be acquired via notices posted in the clinic. If the patient is willing to participate in the planned study, he/she will be fully informed about the aims and methods (especially about the scientific/explorative character of the study), the benefits, risks and the revocability of the participation in the study.

9 Study Procedure

9.1 Procedure of informing and obtaining consent

Patients or subjects can only be enrolled in the study after a written informed consent has been obtained. The written informed consent requires verbal and written explanation to the patients about the aims and methods (including the scientific-explorative character of the study), benefits and risks as well as the revocability of the study participation.

The study participant is clearly informed that withdrawal of consent is possible at any time and without any disadvantage. All study participants will be advised that this study is a purely scientific study without any current diagnostic or therapeutic benefit.

The original informed consent form will be kept in the study folder at the study institution. The participant will be given a copy of the patient/proband information and consent form.

9.2 Measures

After informing the patients, all study participants will be asked to provide information about their existing illnesses, previous operations, and current medication. If available, the electronic patient file will be used for this purpose, otherwise these data will be collected by means of a medical history interview. Of particular interest are diseases, operations and medication related to the vascular system. This is followed by measurement of the ABI. This parameter is used in vascular medicine to estimate the

severity of PAD. For healthy study participants, the measurement of the ABI is to be regarded as a screening examination. Study participation of healthy volunteers requires an unremarkable value in the ABI measurement (the handling of incidental findings during screening is presented in chapter 13). Prior to this measurement, a rest period in lying position of at least 10 minutes should be observed. Measurements of occlusion pressures on both legs and arms are then performed. The examination of the ABI takes a maximum of 20 minutes, including the preceding rest period, and would also be recorded in PAD patients independently of study participation during the inpatient stay as part of routine diagnostics. Afterwards, a CCDS of the femoral arteries is performed at rest. The CCDS is used to determine the flow profile of the examined vessels and allows an estimation of constrictions or occlusions in these. For this purpose, the patient/proband remains lying on the examination couch. Depending on the examination conditions (individual anatomy of the vessels, body size, etc.), this examination takes about 10 minutes. This examination takes place as part of routine vascular surgery diagnostics.

The actual current walking distance is used to classify and categorize the severity of PAD and should be recorded by a treadmill examination. Under medical supervision, the patients/probands are to complete the greatest possible distance on the treadmill at a 12% incline and 3 km/h (standard setting). If the 12% incline is not practicable for the patient, the incline will initially be reduced to 6%. If this is also not practicable, it will be reduced to 0% incline. The walking distance is recorded in meters. Since the first 200 meters in particular are important for the classification of PAD, the examination will be terminated by the study physician when a walking distance of more than 500 meters has been reached. The treadmill examination takes about 15 minutes and is usually performed for patients in stage II as part of routine vascular surgery diagnostics. For patients in stage III or IV, the examination is not part of the routine diagnostics and only takes place within the framework of study participation if the study physician declares this medically justifiable.

All examinations mentioned so far take place in the facilities of the Department of Vascular Surgery.

For the MSOT measurements, the CE-certified MSOT device of the Pediatric and Adolescent Clinic of the University Hospital Erlangen is used. Since the MSOT device is located in the facilities of the Children's Hospital, the patients/probands are transported there in a wheelchair after the examinations mentioned so far. It is

important that there is no physical exertion during the transport, as this could falsify the MSOT values. The transport takes about 15 minutes. Subsequently, MSOT measurements are taken with the MSOT device over a length of about 6 cm in the longitudinal section of the medial head of the gastrocnemius muscle (in patients in the area of the affected leg). Multiple measurements of both legs are performed with different foils applied in a standardized manner.

If necessary, the area of the lower leg to be examined will be shaved to avoid artifacts from dark colored hairs. The ultrasound gel is applied to the calf. Then a foil imprinted with an "N" is applied and fixed. The proband ID is noted on the foil. Above the imprint, an initial static measurement is taken at rest and subsequently a longitudinal measurement is taken, which can be reconstructed in 3D. At least three longitudinal 2D measurements are made or repeated until a promising result is obtained. The same procedure is repeated with a foil imprinted with a trident.

The examination is performed analog to sonography above the corresponding skin layers without further invasive procedures. The anatomical region can be localized by means of built-in B-scan sonography; subsequently, the corresponding optoacoustic signals can be derived. The duration per anatomical region is limited to 5 minutes; the study participants can remain in a relaxed position during the examination; assistance, e.g., breathing maneuvers, is not necessary.

Subsequently, the patient will complete a defined walking distance of 150 meters under medical supervision. The foils printed with tridents remain fixed to the calf muscles for this purpose. Afterwards, the medial head of the gastrocnemius muscle is measured again using MSOT. Therefore, the affected leg of patients is first examined in a static 2D-measurement, then in longitudinal measurements and again in a static 2D-measurement. In healthy probands, the right leg is measured first.

After a second defined walking distance of 150 meters, the unaffected leg is examined in patients and the left leg in healthy probands in the order described above.

In the context of so far unpublished preliminary studies, it was indicated that an active muscle exercise between the two examinations by MSOT causes a change of the perfusion parameters and can possibly unmask a stenosis in the supply area of the lower legs. If the patient is unable to walk 150 meters between the two MSOT measurements due to pre-existing conditions or due to the severity of the PAD stage,

the distance of walking can be reduced stepwise. In this case, an initial attempt should be made to complete a distance of 100 meters. If this is also not feasible, the distance of the walking load is first reduced to 50 meters and finally to 25 meters. In the case of complete inability to walk, standing exercises can be performed as an alternative. In this case, the patient should be instructed to alternate between tiptoe and heel stance for at least two minutes. If this form of muscle exercise is also not possible, patients can sit down and should perform extensions and flexions of the foot over a period of at least two minutes to provoke lower leg muscle exercise between the two MSOT measurements.

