1.4 Protocol establishment

PD Dr. med. [name], [name], [name]

2 Summary

Functional imaging diagnostics is becoming increasingly important due to the steadily growing knowledge of physiological processes in many diseases. Likewise, in peripheral arterial occlusive disease (PAD), new insights into the pathomechanism of the disease are continuously being gained [1]. Similarly, this increases the need for new non-invasive imaging methods that are able to visualize the functional level of the disease progression and thus enables the diagnosis at an early stage.

Recent studies indicate that it may be feasible to use multispectral optoacoustic tomography (MSOT) to visualize hemodynamics and the fibrotic muscle remodeling process in PAD [2]. For a better understanding of the distribution pattern, the exploration of a 3D technique is a next necessary step in imaging. This may show a possible existing heterogeneity of these molecules.

The aim of this exploratory pilot project is to image muscle perfusion of the lower extremity in three dimensions using the MSOT method and to verify its feasibility. The advantage of 3D imaging is, beyond the anatomical topography of the muscle, to map a three-dimensional representation of the perfusion situation based on muscle oxygenation.

For this purpose, six patients of different symptomatic PAD stages and a healthy control of two volunteers will be included and examined by the means of longitudinal MSOT scans in the area of the gastrocnemius muscle. To evaluate the current stage of the disease or to exclude relevant PAD in the healthy control population, non-invasive examination measures commonly used in routine diagnostics of PAD will be applied. In addition to the relevant risk factors, coexisting comorbidities and the current medication, these include the recording of the ankle-brachial index (ABI), color-coded duplex sonographic vascular imaging (CCDS) and a treadmill examination.

3 Responsibilities

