Until now, there are few noninvasive measurement methods besides MSOT that can provide transcutaneous information about 3D muscle perfusion. Even topographic muscle imaging from computed tomographic (CT) or magnetic resonance imaging (MRI) reconstructions carries certain risks despite its routine in daily clinical use. For example, CT examinations require radiation exposure, and MRI examinations exclude patients with certain comorbidities or previous performed surgeries (loose metal parts such as pacemakers) and patients with restlessness.

In this explorative pilot study, a 3D reconstruction of the calf muscle using MSOT techniques to visualize muscle perfusion will be investigated for the first time in a PAD patient group. Patients with different PAD stages and a control collective of healthy volunteers as a comparison group will be included. Different optical patterns offer diverse possibilities for the calculations of the 3D reconstruction. Therefore, this study will also evaluate the feasibility of the two options and analyze the measurements to optimize the 3D procedure.

[figure not shown]

Figure 1: Visualization showing optoacoustic signal of perfusion parameters in 2D scans, from left to right: B-scan ultrasound (b/w RUCT), signal at 800 nm wavelength, Hb signal (blue), HbO₂ signal (red) of the medial muscle head of the gastrocnemius muscle (transversal plane). Unpublished original data.

[figure not shown]

Figure 2: Visualization showing optoacoustic signal of connective tissue structures in 2D scans, from left to right: B-scan ultrasound (b/w RUCT), signal at 800 nm wavelength, collagen signal (turquoise), lipid signal (yellow) of medial muscle head of gastrocnemius muscle (transversal plane). Unpublished original data.

References

1. Signorelli, S.S., et al., *Pathophysiology of chronic peripheral ischemia: new perspectives*. Therapeutic Advances in Chronic Disease, 2020. **11**: p. 1-15.
2. Karlas, A., et al., *Multispectral optoacoustic tomography of muscle perfusion and oxygenation under arterial and venous occlusion: A human pilot study*. Journal of Biophotonics, 2020. **13**(6): p. e201960169.
3. Knieling, F., et al., *Multispectral Optoacoustic Tomography for Assessment of Crohn's Disease Activity*. The New England Journal of Medicine, 2017. **376**(13): p. 1292-1294.

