5.1 Primary/secondary objectives and hypotheses

Primary hypothesis:

- MSOT provides topographic perfusion imaging of the gastrocnemius muscle using 3D reconstruction.

Secondary hypotheses:

- Collected 3D MSOT parameters in muscles of patients with PAD differ visually depending on the clinical severity of PAD, classified according to Fontaine and Rutherford.
- Collected 3D MSOT parameters in muscles of patients with PAD differ quantitatively depending on the clinical severity of PAD, classified according to Fontaine and Rutherford.
- Collected 3D MSOT parameters in muscles of patients with PAD show improved diagnostic accuracy than 2D MSOT measurements.

Primary objective:

- Visualization of a perfusion topogram based on oxygenated hemoglobin in the calf muscle of patients with PAD using 3D MSOT.

Secondary objectives:

- Acquisition of different MSOT values at multiple wavelengths in the range from 660 nm up to 1100 nm in static and longitudinal measurements.
- Acquisition of the quantitative hemoglobin signal (oxygenated/deoxygenated) as unmixed spectrum.
- Acquisition of the quantitative lipid signal as unmixed spectrum
- Acquisition of the quantitative collagen signal as unmixed spectrum
- If an MRA is already available regardless of study participation, validation of the accuracy of the MSOT 3D reconstruction using an overlay.

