7.2 Study arms: intervention/control

Interventions are not planned. The study will be conducted in two stages. First, the presentability of 3D reconstruction of the calf muscle will be tested in two healthy volunteers. Subsequently, a representative patient collective of different PAD stages will be examined with the method.

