7.4 Blinding

The investigator will be blinded during the measurement and data analysis. The blinding of the investigator is done by the investigator only performing the MSOT measurements and not knowing the results from the previous examinations (ABI, CCDS, treadmill, PAD stage).

Blinding of the patients/healthy study participants is not necessary.

[figure not shown]

Figure 3 Graphical presentation of the study flow with the planned measurements.

8 Study Population

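### Longitudinal sweeps may be repeated until one looks promising, with no definition of promising, no required count of attempts and no named analysis sweep

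*Combined protocol and SAP*

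**What the plan says.** The study's purpose is feasibility. Section 2 aims to image calf perfusion in three dimensions "using the MSOT method and to verify its feasibility", and the primary hypothesis in Section 5.1 is that "MSOT provides topographic perfusion imaging of the gastrocnemius muscle using 3D reconstruction". Section 4 adds a second aim concerning the two printed foils: "this study will also evaluate the feasibility of the two options and analyze the measurements to optimize the 3D procedure". Section 6.2 lists reconstruction with the two pattern designs as a secondary outcome.

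Section 9.2 has both legs measured: "Multiple measurements of both legs are performed with different foils applied in a standardized manner". For each foil there is one static scan at rest, then longitudinal sweeps under this rule: "At least three longitudinal 2D measurements are made or repeated until a promising result is obtained". The N foil comes first and the trident foil second. The trident foil stays on during the walk, and longitudinal sweeps are taken again afterwards, with no number given. Sections 9.2 and 10.3 limit the examination to 5 minutes per anatomical region.

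Sections 6, 9.3 and 11 do not ask for the number of attempted or failed sweeps, and do not say which sweep, or which average, supplies the topogram or the quantitative values. Section 12.1 treats raw data as source documents, which would permit a later count but does not call for one. Section 7.4 blinds the investigator by "not knowing the results from the previous examinations (ABI, CCDS, treadmill, PAD stage".

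**The concern.** The rule makes the number of sweeps depend on how the results look. If nobody counts the attempts, a topogram in every participant is compatible both with a method that works on most sweeps and with one that works only after several tries. A later study would need to know which.

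The foil evaluation is exposed in a second way. The rule runs separately for each foil, so one may receive more tries than the other. Two equally good foils can then appear to differ.

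For quantitative values, the absence of a named sweep leaves the choice to be made after the images have been seen. The blinding in Section 7.4 limits selection by disease severity, which is useful, but it cannot prevent selection on the image itself.

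**Working it through.** **Figures in the plan.** Section 8.2 gives "Two healthy volunteers, two patients in PAD stage II, two patients in stage III and two patients in stage IV", so 2 + 2 + 2 + 2 = 8 participants, which matches the stated total. Reading three as the minimum and both legs as measured, the resting sweeps are 8 × 2 legs × 3 = 48 per foil, or 96 for both foils. No post-exercise number can be derived.

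**What is not given.** The documents state no success rate per sweep, no time per sweep and no maximum number of tries. The inputs below are therefore assumptions, shown over a range.

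**Model.** Take one foil on one leg per participant. Let p be the success probability per sweep, r the correlation between sweeps in that unit, and k the number of tries.
- For r = 0: P(at least one success) = 1 − (1 − p)^k.
- For r > 0 (beta-binomial), with s = 1/r − 1: P = 1 − product over j = 0 to k − 1 of [(1 − p)s + j] / (s + j).

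Example with p = 0.5 and r = 0.2, so s = 4. For k = 3, 1 − (2/4)(3/5)(4/6) = 0.800. For k = 6, 1 − 0.200 × (5/7)(6/8)(7/9) = 0.917. The gap is 0.117.

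**Equal foils, 6 tries against 3** (entries for r = 0 / 0.2 / 0.5):

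| p | k = 3 | k = 6 | False gap |
|---|---|---|---|
| 0.3 | 0.657 / 0.574 / 0.465 | 0.882 / 0.740 / 0.558 | 0.23 / 0.17 / 0.09 |
| 0.5 | 0.875 / 0.800 / 0.688 | 0.984 / 0.917 / 0.774 | 0.11 / 0.12 / 0.09 |
| 0.8 | 0.992 / 0.966 / 0.912 | 1.000 / 0.993 / 0.949 | 0.01 / 0.03 / 0.04 |
| 0.9 | 0.999 / 0.989 / 0.962 | 1.000 / 0.998 / 0.979 | at most 0.02 |

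**Success in all 8 participants.** With participants independent, this is the eighth power of the values above.
- p = 0.5: 34% / 17% / 5% with 3 tries and 88% / 50% / 13% with 6, ratios 2.57 / 2.97 / 2.59.
- p = 0.8: 94% / 76% / 48% with 3 tries and 99.9% / 95% / 66% with 6, ratios 1.07 / 1.24 / 1.37.

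**Room for repeats.** Taking one calf as the region, the minimum resting set is 1 static scan plus 3 sweeps per foil, so 8 acquisitions for two foils. If the foils share the 5 minutes, that allows 300/8 = 37.5 s each on average; if each foil has its own 5 minutes, 300/4 = 75 s. If the time points share the limit as well, the average is shorter still. Without a sweep time, the number of repeats that fit is unknown.

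**The case against.** The strongest reply is that the plan promises no success proportion, no claim about all 8 participants and no numerical foil contrast. The primary outcome is the topogram itself, the analysis is mainly descriptive, and the foils are studied in order to optimise the procedure. Section 7.2 begins with a technical trial run: "First, the presentability of 3D reconstruction of the calf muscle will be tested in two healthy volunteers". Retaking images is natural in such work. All of this stands. It lowers the weight of the point but does not remove it, because the study still sets out to verify feasibility and to evaluate two foils, and both judgements rest on these sweeps.

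Success per sweep may also be high: Section 11 selects participants suited to the measurement, and Section 4 cites earlier in-vivo work on the forearm. The table shows that the effect is then close to nil.

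The 5-minute limit does bound repetition, but by time rather than by number, and its scope across foils and time points is not stated. Section 9.3 describes reconstruction as following the scans, so the operator may not see it when deciding to rescan. How closely promising tracks successful reconstruction is therefore unknown.

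A reader might infer that the before/after t-test in Section 11 is biased. The documents do not support that. The one item in Section 6.2 that itself names before and after is the static 2D measurement, which lies outside the repeat rule. Section 6 opens by saying that all MSOT measurements are made before and after walking, so longitudinal values could enter the test, but no passage says that they do. Nor does any passage tie promising to a high signal.

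**Conclusion.** The point holds as a gap in counting and choosing sweeps. The repeat rule depends on the result, its stopping criterion is undefined, attempts need not be reported, and the analysis sweep is not named. As written, the plan can show that a topogram is obtainable, but not how reliably a sweep yields one, and the foils may be compared on unequal effort.

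The size is unknown. Under the assumed model it runs from large (false foil gap up to 0.23 at 30% success per sweep; chance of success in all 8 participants raised 2.6 to 3 times at 50%) to near zero (gap at most 0.02 at 90%). The success rates, the correlations and the 6-against-3 contrast are illustrations, not findings about this study.

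It would go too far to conclude that the primary result is invalid or that repeating sweeps is wrong: a topogram obtained after several tries is still a topogram. Severity is minor to moderate.

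**What to change.** **Section 9.2.** Replace the sentence with wording such as: *Three longitudinal sweeps are taken per foil and leg at rest. All sweeps, including failed ones and any further sweeps taken to optimise the method, are kept and logged by foil, leg and time point.* The sponsor should state the number of post-exercise sweeps; this review does not set one.

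**Before the first participant.** Set a provisional rule for a reconstructable sweep, for example that the foil pattern is detected over the full length of about 6 cm. If the rule is revised after the two volunteers, report their sweeps separately.

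**Section 11.**
- Report reconstructable sweeps over all attempted sweeps, and participants out of 8.
- Compare the foils at rest on the first three sweeps only, and state the fixed order (N before trident) as a limitation.
- If longitudinal values enter a before/after comparison, use the trident foil and the same pre-stated sweep rule at both time points, record the time since exercise, and report the value as missing if no sweep qualifies.

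**Sections 9.2 and 10.3.** Reconcile the repeat rule with the 5-minute limit, stating whether foils and time points share it. Any extra sweeps must stay within that limit.

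**Cost.** A short text change and one log line per sweep: 96 at rest, plus post-exercise sweeps and any extras. No participants are added. The reported success rate may look less favourable.

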3.4 Funding source

Vascular Surgery Department; internal funding pending application for external funding.

4 Scientific Background

Starting in 2021, a CE-certified Multispectral Optoacoustic Tomograph (MSOT) will be available at the University Hospital Erlangen (Children's and Adolescent's Hospital). It will allow transcutaneous in-vivo measurements of soft tissue. Comparable to sonography, this allows noninvasive, quantitative imaging of the constitution and oxygenation of target tissues such as muscles.

In MSOT, similar to conventional sonography, a transducer is placed on the skin and instead of sound, energy is delivered to the tissue through flashlights. This leads to a constant alternation of minimal expansions and contractions (thermoelastic expansion) of individual tissue components or molecules. The resulting sound waves can be detected by the same examination probe. Previous studies have shown that quantitative determination of hemoglobin can provide information on blood flow and inflammatory activity in the intestine of patients with Crohn's disease [3, 4]. In the CE-certified MSOT device (Acuity Echo, iThera Medical GmbH, Munich), a spectrum of laser light can be used, which enables the detection of hemoglobin and its oxygenation levels as well as the detection of other markers like collagen and lipid, which has already been successfully measured, validated and reproduced in 2D imaging in pre-studies. Figures 1 and 2 show examples of the feasibility of this imaging method with selected MSOT parameters as examples.

Holzwarth et al. were already able to gain knowledge about the 3D reconstruction from 2D photoacoustic image slices using an optical pattern and the method's feasibility using phantoms as well as in-vivo measurements of the forearm in healthy volunteers [5]. This leads to the evaluation of the method as a diagnostic application for muscular perfusion imaging in patients with vascular dysfunction.

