4. Waldner, M.J., et al., *Multispectral Optoacoustic Tomography in Crohn's Disease: Noninvasive Imaging of Disease Activity*. Gastroenterology, 2016. **151**(2): p. 238-40.
5. Holzwarth, N., et al., *Tattoo tomography: Freehand 3 D photoacoustic image reconstruction with an optical pattern*. International Journal of Computer Assisted Radiology and Surgery, 2021. **16**: p. 1101-1110.

5 Study Objectives

The aim of this pilot study is to implement a three-dimensional reconstruction of the perfusion situation based on two-dimensional longitudinally measured MSOT scans to visualize the topographical distribution of oxygenated hemoglobin in the calf muscle using MSOT.

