10.4 Statement on medical justifiability

Based on previous experience in adult patients, the risk of the occurrence of adverse events is considered to be extremely low. No central organs are examined in this study,

but only measurements on extremities are performed - this leads to a further significant reduction of a possible residual risk. The examination will be performed by persons who are familiar with the device and the measurement method.

11 Statistical Methodologies

Due to the explorative character of the pilot project, mainly a descriptive statistical evaluation of the collected parameters will be performed. A case number of 8 study participants will be chosen to test the feasibility of the 3D method initially. A sample size calculation will not be done. In order to quantitatively classify the results, individual parameters of the study will be compared with values from previous studies on the MSOT procedure in patients with PAD. The MSOT parameters are compared before and after muscle exercise using a paired-samples t-test. The selection of probands will be standardised with one male and one female per stage. Due to the small number of cases, probands who are suitable for MSOT measurements are selected. The criteria include little subcutaneous fat tissue, light skin colour and less hair. Therefore, the selection of probands is not representative of the normal population.

12 Data Management and Data Privacy

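### The repeat resting sweeps have no stated use, so the 3D HbO2 map is not checked against sweep-to-sweep error, and the analysed sweep may be chosen on its result

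*Combined protocol and SAP*

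**What the plan says.** Section 5 gives the aim as a 3D reconstruction to "visualize the topographical distribution of oxygenated hemoglobin in the calf muscle using MSOT", and the primary hypothesis in Section 5.1 is that this gives topographic perfusion imaging. The Summary (Section 2) justifies moving to 3D by possible heterogeneity.

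Section 9.2 sets out the resting acquisition. With the N foil in place, "At least three longitudinal 2D measurements are made"; with its second half, the sentence reads "At least three longitudinal 2D measurements are made or repeated until a promising result is obtained". Then, "The same procedure is repeated with a foil imprinted with a trident". On laterality: "Multiple measurements of both legs are performed with different foils applied in a standardized manner". After walking, with only the trident foil left on, the leg is scanned statically, "then in longitudinal measurements and again in a static 2D-measurement"; the number of post-exercise sweeps is not given.

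In Section 11, "mainly a descriptive statistical evaluation of the collected parameters will be performed", together with a comparison with values from previous studies and a paired t-test before versus after exercise. The outcome lists in Sections 6 and 9.3 contain no repeatability or agreement measure. No section says which sweep enters the analysis or whether sweeps are averaged.

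**The concern.** A handheld sweep reconstructed in 3D always produces some spatial pattern, whether it comes from the muscle or from variation in contact, speed and registration. The minimum evidence that the pattern belongs to the leg is that it comes back when the same resting leg is swept again. The plan collects the data for that check but specifies no use for them, so the primary hypothesis has no criterion that it could fail.

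The second half of the acquisition sentence makes this worse. The number of sweeps is open-ended, and the reason to stop may be the look of the result. If only the favoured sweep is kept, the information on repeatability is lost and the retained map is a selected one.

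**Working it through.** **Does anything else in the documents supply the check?**

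- Section 4 says that the markers were "successfully measured, validated and reproduced in 2D imaging in pre-studies". That covers 2D, not the 3D map.
- The cited 3D work (Section 4) is a feasibility report in phantoms and healthy forearms.
- The MRA overlay (Section 5.1) is done only where an MRA already exists, and it concerns accuracy.
- Section 4 promises to evaluate the two foil patterns and optimise the procedure, but gives no measure for doing so.
- The t-test in Section 11 compares before with after exercise. It does not compare resting sweeps with one another.

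So the check is absent from the plan as written.

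**What could the repeats deliver?** The plan has no figure to reproduce here: Sections 8.2 and 11 state that no sample size was calculated. The inputs are 8 participants (Sections 8.2 and 11), 2 legs, 2 foils and a minimum of 3 resting sweeps (Section 9.2).

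- Resting sweeps: 8 × 2 × 2 × 3 = 96, or 48 per foil.
- Degrees of freedom for the within-leg SD, per foil: 8 × 2 × (3 − 1) = 32.
- 95% limits as multiples of the estimate are √(df/χ²₀.₉₇₅) and √(df/χ²₀.₀₂₅). For 32 df these are √(32/49.48) = 0.80 and √(32/18.29) = 1.32.
- With one leg per participant: 8 × (3 − 1) = 16 df, limits 0.74 to 1.52. Section 9.2 mentions the affected leg in one sentence and both legs in the next, so this is the fallback.
- Pooling both foils would give 64 df and limits of 0.85 to 1.21. That treats the two patterns as equally precise, and comparing them is one of the study's outcomes, so the per-foil figure is the one to use.

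These limits assume a common within-leg SD across legs, people and stages. No comparable figure can be given for agreement of the spatial profile, because the documents give no variances.

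**How much could selection matter?** As an illustration, assume that a promising sweep means the one with the highest signal and that sweeps vary normally. The expected value of the retained sweep is then above the leg's mean by 0.85 sweep SD for the best of 3, 1.16 for the best of 5 and 1.54 for the best of 10 (simulated). If promising means only technically usable, this shift need not arise.

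**Would repeatability rescue the stage comparison?** With two people per stage and the variance pooled over the three PAD stages, df = 3 × (2 − 1) = 3. The 95% half-width for a difference between two stages is t × SD × √(1/2 + 1/2) = 3.18 SD. Averaging three sweeps multiplies this by √(ρ + (1 − ρ)/3), where ρ is the single-sweep intraclass correlation. The documents do not give ρ. Assumed values of 0.5, 0.7 and 0.9 give 2.60, 2.85 and 3.07 SD. Sweep error is not the main limit there.

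**The case against.** The strongest reply is that this is an exploratory feasibility study whose stated objective is visualisation, that the repeats are attempts to obtain a usable sweep and not a replicate design, and that a descriptive evaluation does not rule out an SD or CV. Much of this is fair. The right statement is that no use of the repeats is specified, not that they will go unused. The wording also does not show that sweeps will be picked for favourable results; it only permits it. Section 7.4 blinds the investigator to PAD stage, which limits selection by stage but not selection for a convincing map. The exploratory label does not remove the point, because the remedy is itself descriptive.

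Three stronger readings are tempting, and the documents do not support them.

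- A reader might infer that the missing analysis is what prevents stage differences from being interpreted. With two people per stage, person-to-person variation is the limit, and it would remain after perfect repeatability.
- A reader might turn the resting within-leg SD into a threshold for a real exercise change, using 1.96 × √2 = 2.77 times that SD. The resting sweeps are taken at rest with the foil in place. They leave out foil displacement and drift over the walk, so such a threshold is likely too low. Only the trident foil is scanned after exercise, and the documents do not say whether sweeps are averaged.
- A reader might take recurrence of the pattern as proof of perfusion structure. Fixed sources under an unmoved foil, such as overlying fat, coupling or the imprint, could recur as well.

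**Conclusion.** The point holds for the primary hypothesis. The plan requires repeat resting sweeps but specifies no analysis that shows the 3D HbO2 map recurring, and its stopping wording lets the analysed sweep be chosen on its result. The gap lies in the analysis plan and the retention rule, not in the size of the study: 32 df per foil give an SD known to within 0.80 to 1.32 times the estimate. This rests on three usable sweeps per foil and leg, both legs scanned, and a common within-leg SD.

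What can be learned is within-session repeatability under a fixed foil. It is necessary but not sufficient evidence of true perfusion structure. The change is worth making because the answer bears directly on the primary aim and costs little.

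**What to change.** **Section 9.2.** Replace the either/or wording with at least three resting sweeps per foil and leg in every case, within the existing examination-time limit. Keep all sweeps. Record their number and any technical failures with the reason. Choose the analysed sweeps by a rule that does not depend on the result, for example the first three that can technically be reconstructed.

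**Section 11.** For each foil separately, report:

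- agreement between sweeps of the slice-wise HbO2 profile along the roughly 6 cm scanned;
- within-leg SD and CV of each 3D parameter.

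Also report N-versus-trident agreement in the same leg, noting that it mixes pattern, change of foil and order, since the N foil always comes first. Add a sentence that these are within-session figures under a fixed foil, that they do not support conclusions about stage, and that they are not a threshold for exercise change.

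**Cost.** About 96 resting volumes to reconstruct (the documents do not say how many are planned now), storage of all sweeps and a few sentences of text. Added scan time is little or none, since three sweeps are already the stated minimum; there would be some wherever fewer would otherwise have been taken.
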